7.6.3. Screening

Information on subject demographics, skin pigmentation using Massey scale, self-identified race/ethnicity, surgical history, and medical history including concurrent medications within the last 90 days will be collected.

Study subjects of differing levels of skin pigmentation will be enrolled in the study. When applicable, subjects with varying demographics e.g., skin pigmentation, gender, etc. may be preferentially recruited to create a more balanced population.

7.6.4. Data Collection Procedure

7.6.4.1. A Masimo RD SET® neonatal sensor will be placed on the subject's foot, depending on subject's weight, following manufacturer's DFU and the study's procedure manual. Continuous data from the pulse oximeter will be collected from the Masimo Radical-7 (or comparable) with the Masimo Root Monitoring System.

7.6.4.2. Prior to the placement of INVSENSOR00061, the subject will be observed for crying, restlessness, etc., for approximately [REDACTED] Observations will be recorded on the case report form (CRF).

7.6.4.3. After approximately [REDACTED] INVSENSOR00061 will be placed on the opposite foot of the Masimo RD SET® neonatal sensor.

7.6.4.4. An ambient shield(s) will be used to reduce optical interference between sensors.

7.6.4.5. The Masimo RAM® sensor, if used, will be placed on the subject's chest to measure continuous respiration rate.

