7.6.4.6. The subject will then be observed for approximately [REDACTED]

7.6.4.7. After five minutes of observation, INVSENSOR00061 will be paired via Bluetooth connection to Masimo data collection software on a laptop or phone. Upon successful Bluetooth pairing of the investigational device, data collection will be initiated on the data collection software and data will be obtained continuously (SpO₂, PR, RR_p, temperature, etc.).

7.6.4.8. Data will be collected for approximately [REDACTED] using the data collection software.

7.6.4.9. During this timeframe, the subject's temperature, and manual respiratory rate count for [REDACTED] if required, may be recorded approximately every five minutes.

7.6.4.10. Sensor placement locations, sensor ID/lot number, subject's reaction prior to and after sensors placement, observations during data collection, and other relevant information will be recorded in the CRF.

7.6.4.11. The subject's parent or legal guardian will be asked to complete a survey about their observations and experiences with the device. See Sample survey in Appendix A.

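### In infants given the optional RAM chest sensor, the before/after behaviour record cannot cleanly separate a reaction to the bootie from a reaction to RAM

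*Combined protocol and SAP*

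**What the plan says.** The order of steps in section 7.6.4 of the protocol is as follows.

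- **7.6.4.1:** "A Masimo RD SET® neonatal sensor will be placed on the subject's foot, depending on subject's weight". The reference sensor is therefore on before any behaviour is observed.
- **7.6.4.2:** "Prior to the placement of INVSENSOR00061, the subject will be observed for crying, restlessness, etc., for approximately" a redacted period, with the findings entered on the CRF.
- **7.6.4.3:** "INVSENSOR00061 will be placed on the opposite foot of the Masimo RD SET® neonatal sensor", so the bootie goes on once the baseline has been observed.
- **7.6.4.4:** "An ambient shield(s) will be used to reduce optical interference between sensors". No foot and no moment of application are given.
- **7.6.4.5:** "The Masimo RAM® sensor, if used, will be placed on the subject's chest to measure continuous respiration rate", which in step order comes later than the bootie.
- **7.6.4.6:** "The subject will then be observed for approximately" a redacted period. Step 7.6.4.7 puts Bluetooth pairing after five minutes of observation.
- **7.6.4.10:** the CRF items include "subject's reaction prior to and after sensors placement, observations during data collection".

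Section 7.4 lists the RAM sensor as optional. Section 7.1 bases the confirmation of form, fit and function on whether the supported parameters can be read once the device is on the foot. Section 8 describes no analysis of the behavioural observations.

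**The concern.** The baseline observation is tied by name to the placement of INVSENSOR00061, and the reference sensor is already on by then. The natural reading is that the bootie is meant to be the one thing that changes between the two observations. A chest sensor applied in the same interval breaks that contrast for every infant who gets one.

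The error can run either way. Fussing caused by exposing the chest and applying RAM can be entered as a reaction after the bootie, and a real reaction to the bootie can be put down to RAM. Because RAM is optional and no rule says who receives it, what lies between the two observations may also differ from infant to infant.

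At stake is the descriptive record of how infants tolerate the bootie. No control group is described, so apart from the parent survey (7.6.4.11) this within-infant comparison is the only structured behavioural evidence on the device.

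**Working it through.** No arithmetic in the plan bears on this point, and there is no figure to reproduce. The check is to list what is on the infant at each observation, taking the steps in their numbered order.

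| Item | Step | On at baseline (7.6.4.2)? | On at second observation (7.6.4.6)? |
|---|---|---|---|
| RD SET reference sensor | 7.6.4.1 | Yes | Yes |
| INVSENSOR00061 bootie | 7.6.4.3 | No | Yes |
| Ambient shield(s) | 7.6.4.4 | Not stated; step order suggests no | Yes, by step order |
| RAM chest sensor | 7.6.4.5 | No | Yes, if used |

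1. The reference sensor is present in both periods, so its presence does not contribute to the before/after difference.
2. In an infant without RAM, the difference reflects the bootie and possibly the shield.
3. In an infant with RAM, the difference reflects the bootie, RAM and possibly the shield. No observation is scheduled between 7.6.4.3 and 7.6.4.5 that would split them.
4. The reaction item in 7.6.4.10 is worded for sensors in the plural, and no step asks staff to say which item the infant reacted to.
5. The redactions in 7.6.4.2, 7.6.4.3 and 7.6.4.6 hide durations, not order, so they do not affect steps 1 to 4.

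On size, let *b* be the chance that the bootie unsettles an infant, *r* the share of infants given RAM, and *p* the chance that RAM unsettles an infant, acting independently of the bootie. The recorded post-placement rate would be 1 − (1 − b)(1 − rp), which exceeds *b* by (1 − b)rp. The documents give none of *b*, *r* or *p*. If RAM is never used (r = 0) or never disturbs an infant (p = 0), the excess is zero. The expression also ignores crying already present at baseline. It shows what the distortion depends on but gives no estimate of it.

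**The case against.** The strongest answer is that the study does not judge the device on this measure. Section 7.1 rests on obtaining readings, section 8 sets no reaction rate or comfort criterion, and the remark about comfort in section 3 belongs to a figure caption describing the device. This stands, and it limits the point to descriptive data. It does not make the data idle: the protocol schedules two observation periods and a CRF item for them, and section 8 justifies the sample size partly by human factors and usability.

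Second, 7.6.4.10 also calls for sensor locations, sensor identification and other relevant information. RAM infants can probably be identified, and staff could note when fussing began. The CRF layout and the procedure manual are not in the documents, so item-level attribution may exist there. This stands in part. Knowing who wore RAM allows those infants to be looked at separately, but it does not show which item one of them reacted to.

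Third, putting RAM on earlier may move handling distress into the baseline. That is possible but minor, since handling for the reference sensor already precedes baseline. An uncontrolled before/after comparison in infants also stays open to time, hunger and handling in general, whatever the order.

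Two stronger readings are tempting. A reader might infer that the shield is certainly applied between the two observations. Step 7.6.4.4 gives neither time nor foot, and a shield could already be on the reference foot, so this is only implied by position. A reader might also infer that the bootie's reaction rate will be inflated by some stated factor. Any such factor would rest wholly on assumed inputs, for a rate the plan never sets out to estimate.

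**Conclusion.** The point holds for infants who receive RAM. As the steps are written, their before/after behavioural record cannot cleanly separate a reaction to INVSENSOR00061 from a reaction to the chest sensor. This does not mean that every recorded reaction is contaminated, since an infant may not react to RAM at all.

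The consequence is confined to the descriptive tolerability record; this finding does not touch the readings-based assessment in section 7.1. Its size cannot be estimated from the documents.

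The conclusion assumes that staff follow the numbered order and that the CRF does not already attribute reactions by item. It is a cheap improvement to make before enrolment, because attribution that is not recorded at the bedside cannot be recovered in analysis.

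**What to change.** - Move RAM placement, if used, into 7.6.4.1 alongside the reference sensor, before the baseline observation in 7.6.4.2. Do the same for any shield on the reference foot. Both are then present in both periods, as the reference sensor already is.
- Keep any shield on the bootie foot together with the bootie, so that the second observation covers the configuration used for data collection.
- In 7.6.4.10, have the CRF record which items were on at each observation, and the reaction after INVSENSOR00061 placement specifically.

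Placing RAM after the second observation instead would also separate the two, but it would disturb the infant just before the readings on which section 7.1 depends, so it is not recommended.

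The cost is a reordering of existing steps, matching edits to the procedure manual, and one or two CRF fields. No extra infants, devices or visits are needed. The downside is slightly more handling and set-up time before the baseline observation.

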7.6.4.6. The subject will then be observed for approximately [REDACTED]

7.6.4.7. After five minutes of observation, INVSENSOR00061 will be paired via Bluetooth connection to Masimo data collection software on a laptop or phone. Upon successful Bluetooth pairing of the investigational device, data collection will be initiated on the data collection software and data will be obtained continuously (SpO₂, PR, RR_p, temperature, etc.).

7.6.4.8. Data will be collected for approximately [REDACTED] using the data collection software.

7.6.4.9. During this timeframe, the subject's temperature, and manual respiratory rate count for [REDACTED] if required, may be recorded approximately every five minutes.

7.6.4.10. Sensor placement locations, sensor ID/lot number, subject's reaction prior to and after sensors placement, observations during data collection, and other relevant information will be recorded in the CRF.

7.6.4.11. The subject's parent or legal guardian will be asked to complete a survey about their observations and experiences with the device. See Sample survey in Appendix A.

7.7. Monitoring Plan

As the sponsor of this clinical investigation, Masimo Corporation is required by 21 CFR Part 812, of the Food and Drug Administration regulations to monitor and oversee the progress of the investigation. The monitor(s) assigned by Masimo Corporation to this task will be trained on departmental Standard Operating Procedures (SOPs) on conduct and monitoring of sponsored studies.

In accordance with good clinical practices guidelines, there will be at least three scheduled monitoring visits to ensure overall regulatory compliance of the study:

- An initiation visit, prior to any subject enrollment to confirm site readiness, and to document training on the study protocol and procedures, and use of equipment.
- At least one monitoring visit during initial enrollment, and/or every 2-4 weeks thereafter until completion of the study.
- A final close out visit after the last subject had finished the study.

The monitor will contact and visit the investigator and will be allowed, on request, to have access to all source documents needed to verify the entries in the CRFs and other GCP-related documents (IRB approvals, IRB correspondences, and ICFs), provided that subject confidentiality is maintained in agreement with HIPAA regulations. The Investigator will provide the monitor access to all necessary records to ensure the integrity of the data (21 CFR 812).

It will be the monitor's responsibility to inspect the CRFs at regular intervals throughout the study, to verify the adherence to the CIP and the completeness, consistency, and accuracy of the data being entered on them.

During each visit, the monitor will also verify adherence to the inclusion/exclusion criteria, and documentation of SAEs/SADEs and protocol deviations/violations and check the CRF against source documentation.

After each visit, the monitor will provide a monitoring report to the Investigator within four weeks of visit completion. The monitoring report will detail findings and open action items observed during the visit. It is the responsibility of the PI and study coordinator(s) to respond to the findings of the monitoring report and complete any open action items as soon as possible but no later than 60 days of

receiving the monitoring report. Any open action items not completed within the time allowed may be sufficient grounds for study site suspension or termination; it will be up to the sponsor to determine whether any incomplete action items are sufficient grounds for suspension or termination.

Depending on the quality of the data and/or changes to factors affecting subject safety, additional monitoring visits may be necessary at the sponsor's discretion.

8. STATISTICAL DESIGN AND ANALYSIS

This is a single center prospective study that will use a convenience sampling of 30 subjects. A minimum of 30 subjects are being targeted for this study because it exceeds the 15 typically recommended by the FDA to evaluate the human factors and usability of a device and the number is aligned to the number of subjects calculated by Masimo in which the statistical value of additional subjects diminishes in the Arms error distribution analysis.

8.1. Expected Dropout Rates

Subjects may not complete the study for various reasons, such as clinical screening test failure, at the investigator's or study staff's discretion, or because the subject does not want to continue the study. Due to the short duration and simple, noninvasive procedures of this study, there are limited expected dropouts.

However, the sample size may be increased to account for dropout rates during the study.

9. DATA MANAGEMENT

9.1. Data Management and Confidentiality

All documents associated with this protocol will be securely stored in a physical location or on password-protected computers. The confidentiality and retention of these documents will be protected to the extent provided and required by the law. All data will be de-identified before any statistical analysis. Only de-identified data will be shared with Masimo for research purposes stated in this protocol. Data collected by the eCRF data capture software will be shared with Masimo via a secure, password-protected server that only study staff and Masimo study team members will have access to. Data will be retained for a minimum of two years following completion of the final analysis.

9.2. Source Documents

Source data is all information, original records of clinical findings, observations, or other activities in a clinical trial necessary for the reconstruction and evaluation of the trial. Source data are contained in source documents. Examples of these original documents and data records include: hospital records, clinical and office charts, laboratory notes, memoranda, recorded data from automated instruments, and copies or transcriptions certified after verification as being accurate and complete.

9.3. Case Report Forms

The site shall capture study data in case report forms (CRFs) for each subject enrolled, to be provided to the sponsor. CRFs may be in paper or electronic format through electronic data capture (EDC) software. Masimo shall ensure that systems used for electronic CRFs are compliant with the requirements of 21 CFR Part 11 and ISO / IEC 27001 certification. The CRFs will be completed and signed by the PI or delegate. This also applies to those subjects who fail to complete the study.

If a subject withdraws from the study, the reason must be noted on the CRF. The eCRFs are to be completed on an ongoing (weekly) basis. CRF entries and corrections will only be performed by study site staff, authorized by the investigator. For paper CRFs, entries and corrections to the CRF will be made following good documentation practices (GDP).

The CRF may include the following information, including but not limited to: inclusion/exclusion criteria, whether subject consent was obtained before start of study, demographic information, device readings, and if occurrence of any adverse event, protocol deviation, and device deficiencies, etc. The CRFs will be signed by the PI or delegate to attest that the data are complete and accurate.

CRF entries will be checked by the study monitor and any errors or inconsistencies will be queried to the site on an ongoing basis. Any changes made within an electronic CRF will be tracked by audit trail. Any changes on a paper CRF will be made directly on the CRF and will be initialed and dated by the person making the change. Query resolution will be assessed and confirmed by study monitor during site visit.

9.4. Data Transfer and Storage

Original paper CRFs will be stored in a secure location at the site. Copy of the original paper CRFs may be scanned and sent to sponsor. If using electronic CRFs, the site staff will be assigned unique usernames and passwords for data security. Final copies of the electronic CRFs in EDC are stored on a secure server.

Only authorized sponsor personnel will have access to study data, and will move it to a secure and backed-up drive at Masimo.

CRFs will be checked for completeness and if there are inconsistent or missing data points, queries will be generated. If delegated study staff are to correct the paper CRF, they shall follow GDP practices to strike through old entry, add in new entry, initial and date it, and provide the corrected information to sponsor. Corrections made to electronic CRFs will be tracked by audit trail and require PI or delegate sign-off.

9.5. Record Retention

Study data will be retained for the necessary period of time as required by the institution's regulations. Study records shall be retained for a minimum of two years after study closure. The institution's own retention policies and regulations may apply in addition to the minimal requirement.

10. AMENDMENTS TO THE CLINICAL INVESTIGATION PLAN

Any changes made to the clinical investigational plan/study protocol will be documented by way of an amendment. Before submitting a protocol amendment to the IRB, the protocol amendment must be agreed upon and signed by both the PI and the sponsor. The protocol amendment will be submitted to the IRB for approval. At a minimum, a redline version and a clean version of the new protocol amendment will be kept on file by the PI and the sponsor. Protocol amendments will need to be version controlled. Both PI and sponsor will retain the IRB approval letter as confirmation that the protocol amendment was approved.

11. DEVIATIONS FROM CLINICAL INVESTIGATION PLAN

Deviations from the protocol must receive both sponsor and the investigator's IRB/ethics committee approval before they are initiated, with the exception that under emergency circumstances, deviations from the *Clinical Investigation Plan* to protect the rights, safety and well-being of human subjects may proceed without prior approval of the sponsor or the IRB/ethics committee.

Any protocol deviations initiated without sponsor and the investigator's IRB/ethics committee approval that may affect the scientific soundness of the study, or affect the rights, safety, or welfare of study subjects, must be documented and reported to the sponsor and to the investigator's IRB/ethics committee as soon as a possible, but no later than 5 working days after the occurrence of the protocol deviation. In addition to documenting deviations on the CRF, the *Protocol Deviation Form* may also be used. If protocol deviations continue to occur frequently at a study site, a corrective and preventive action (CAPA) may be opened by the sponsor.

Withdrawal of IRB approval: An investigator shall report to the sponsor a withdrawal of approval by the investigator's reviewing IRB as soon as possible, but no later than five working days of the IRB notification of withdrawal of approval.

12. DEVICE ACCOUNTABILITY

12.1. Receipt of Study Device

Upon receipt of the study device supplies, an inventory must be performed and the device accountability log filled out and signed by the person accepting the shipment. It is important that the designated study staff counts and verifies that the shipment contains all the items noted in the shipment inventory. Any damaged or unusable study devices in a given shipment will be documented in the study

files. The investigator must notify the study sponsor of any damaged or unusable study devices that were supplied to the investigator's site.

12.2. Use of Study Device

Use of device will be documented in a CRF module for each subject. Any unused devices must be returned to the sponsor at the end of the study or before product expiration date.

12.3. Return or Destruction of Study Device

At the completion of the study, there will be a final reconciliation of study devices shipped, devices used, and devices remaining. This reconciliation will be logged on the device accountability log. Any discrepancies noted will be investigated, resolved, and documented prior to return or destruction of unused study devices. Devices destroyed onsite will only be upon written instruction from the sponsor and will be documented in the study files. When a Masimo device deficiency is observed, every effort should be made to return the device and its packaging to the sponsor in a timely manner.

13. STATEMENTS OF COMPLIANCE

This document is a clinical investigational plan for a human research study sponsored by Masimo Corporation. The study will be conducted in accordance with the ethical principles that have their origin in the Declaration of Helsinki. By participating in the study, the Investigator agrees to adhere to all stipulations of this protocol, the conditions of the IRB or Research Ethics Committee approval, federal and local regulatory requirements, 21 CFR 812, ISO-14155, ICH GCP guidance.

The protocol, ICFs, recruitment materials, and all subject materials will be submitted to the IRB for review and approval. Approval of both the protocol and the consent form must be obtained before any subject is enrolled. Any amendment to the protocol will require review and approval by the IRB before the changes are implemented to the study.

14. INFORMED CONSENT PROCESS

See subsection on *Informed Consent Process* under *Study Procedures*.

15. ADVERSE EVENTS, ADVERSE DEVICE EFFECTS, AND DEVICE DEFICIENCIES

15.1. Definitions

The definitions for adverse event, adverse device effect, serious adverse event, serious health threat, serious adverse device effect, and unanticipated adverse device effect, device deficiencies are provided below (ISO 14155, 21 CFR 812.3(s)).

- **adverse event:** untoward medical occurrence, unintended disease or injury, or untoward clinical signs (including abnormal laboratory findings) in subjects, users or other persons, whether or not related to the investigational medical device and whether anticipated or unanticipated (ISO 14155)
- **adverse device effect:** adverse event related to the use of an investigational medical device
- **serious adverse event:** adverse event that led to any of the following:
 - a) death
 - b) serious deterioration in the health of the subject, users, or other persons as defined by one or more of the following:
 - 1) a life-threatening illness or injury, or
 - 2) a permanent impairment of a body structure or a body function including chronic diseases, or
 - 3) in-subject or prolonged hospitalization, or

- 4) medical or surgical intervention to prevent life-threatening illness or injury, or permanent impairment to a body structure or a body function,

- c) fetal distress, fetal death, a congenital abnormality, or birth defect including physical or mental impairment

Note: Planned hospitalization for a pre-existing condition, or a procedure required by the *Clinical Investigation Plan*, without serious deterioration in health, is not considered a serious adverse event.

- serious health threat: signal from any adverse event or device deficiency that indicates an imminent risk of death or a serious deterioration in the health of subjects, users or other persons, and that requires prompt remedial action for other subjects, users or other persons.

Note: This would include events that are of significant and unexpected nature such that they become alarming as a potential serious health hazard or possibility of multiple deaths occurring at short intervals.

- serious adverse device effect: adverse device effect that has resulted in any of the consequences characteristic of a serious adverse event
- unanticipated serious adverse device effect: serious adverse device effect which by its nature, incidence, severity or outcome has not been identified in the current risk assessment

Note: Anticipated serious adverse device effect (ASADE) is an effect which by its nature, incidence, severity or outcome has been identified in the risk assessment.

- device deficiency: inadequacy of a medical device with respect to its identity, quality, durability, reliability, usability, safety or performance

Note 1: Device deficiencies include malfunctions, use errors, and inadequacy in the information supplied by the manufacturer including labeling.

Note 2: This definition includes device deficiencies related to the investigational medical device or the comparator.

